7.12 Medical Care after Study Participation

Upon the subject's termination (premature or planned) in the clinical study, it is up to the subject him/herself and the parents/caregivers, preferably in agreement with the treating physician, to determine their future treatment needs from the following options:

- return to the device used prior to the study or
- start/continue with ACCU-CHEK® Connect DMS
- use any other suitable device available on the market

8 Risk/Benefit Analysis of the Investigational Device and Clinical Investigation

8.1 Potential Risks

During participation in this clinical study, subjects may encounter the following known potential risks of diabetes management therapy:

- Possible hypoglycaemia.
- Possible hyperglycaemia which might progress to ketosis and diabetic ketoacidosis (DKA).
- Mild discomfort and soreness, risk of infection from multiple finger sticks
- Anxiety over recording SMBG values that maybe out of the expected target ranges.

The above risks are an integral part of diabetes therapy and applied in daily practice. It has to be underlined that subjects face the same risks as listed during their routine therapy. The likelihood of serious events occurring is considered uncommon.

8.2 Minimization of Risks

The Sponsor has minimized the potential of the above risks to occur by:

- Selection of qualified Investigators consulting study subjects during the scheduled visits.
- Selection of subjects, parents/caregivers experienced in diabetes management therapy
- Subjects are advised not to change their current MDI diabetes therapy without consulting their physician (Investigator).

8.3 Potential Benefits

The study subjects and their families may experience the following potential benefits while participating in this study:

- Subjects and their families may be motivated to learn more about diabetes and to have better discussions of potential issues with their health care providers.
- Subjects and their families may gain personal satisfaction and decreased diabetes distress from participating in this study.
- Subjects may reduce their HbA1c from participating in this study
- The following will be provided during the study at no charge to subjects and their families:
 - ACCU-CHEK[®] Connect Diabetes Management App
 - o ACCU-CHEK® Aviva Connect BG Meter and consumables
 - Smartphones, if applicable
- At study completion, subjects and families in the intervention group may elect to keep and use the investigational device; except the study provided Smartphone, if applicable. Regardless of group assignment each family will receive a gift card for the completion of Visit 1, 3 and 4 (total if all visits completed).

9 Adverse Events Recording and Reporting

9.1 Definitions of Adverse Events

The definitions are based on ISO 14155:2011(E) and respective sections CFR Title 21 for Medical Device Studies.

9.1.1 Adverse Event

An Adverse Event (AE) is any untoward medical occurrence, unintended disease or injury, or untoward clinical signs (including abnormal laboratory findings) in subjects, users or other persons, whether or not related to the investigational medical device.

In addition, this definition includes events related to the procedures involved. For users or other persons, this definition is restricted to events related to investigational medical devices.

9.1.2 Serious Adverse Event

A Serious Adverse Event (SAE) is any AE that fulfils at least one of the following criteria:

- Led to death.
- Led to a serious deterioration in the health of a subject resulting in:
 - o A life-threatening illness or injury, or
 - o A permanent impairment of a body structure or a body function, or
 - An in-patient or prolonged hospitalization, or
 - A medical or surgical intervention to prevent life-threatening illness or injury or permanent impairment to a body structure or a body function.
- Foetal distress, foetal death or a congenital abnormality or birth defect.

A planned hospitalization for a pre-existing condition, or a procedure required by the study procedure, without serious deterioration in health, is not considered an SAE.

9.2 Definition of Hypoglycemia, Hyperglycemia Episodes and Diabetic Ketoacidosis

Hypoglycemia and hyperglycemia can be symptomatic or asymptomatic and are subset of AEs occurring within Diabetes studies.

Any hypoglycemia or hyperglycemia episode which occurs during the course of the study will be documented by the subject him-/herself in his/her individual Subject Diary, if applicable, or will be defined specifically by the study procedure e.g. in the visit description of this study protocol.

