- Download SMBG data using existing site process and discuss SMBG download with patient and parent/caregivers and collaboratively agree on therapy changes (pharmacologic and/or behavioral) and modify SMBG regimen, if needed.
- Download current BG meter using Diasend for eCRF data
- Schedule appointment for week one phone call (Visit 2) and 3 months (Visit 3)
- Record number of days missed from work (parent/caregiver)/school (child with diabetes) that
 are diabetes related in previous 3 months and indicate reason (doctor appointments, illness or
 other.
- Discuss and record current prescribed therapy (pharmacologic and/or behavioral) and prescribed SMBG regimen.
- Record any adverse events (AEs) since last visit if not done immediately
- Record all relevant data in the eCRF

Intervention Sites, only

- Dispense ACCU-CHEK[®] Connect DMS and record serial number of BG meter(s)
- Dispense Smartphone to child/adolescent (if applicable)
- Set up ACCU-CHEK[®] Connect DMS for connectivity, portals & invitations
- Provide training in the use of the system
- register current operating system of smart phone with version number
- Dispense Call Center Card and instruct in reporting of malfunctions/complaints with ACCU-CHEK® devices

7.3 Visit 2 – Phone Call one week after Visit 1

Study procedures include the following assessments:

- Record any adverse events (AEs) since last visit, if this has not been done immediately
- Record malfunctions/complaints of any device, if any
- Intervention group: Follow-up with parents/caregivers and child with diabetes to identify issues/obstacles associated with system in use
- Record all relevant data in the eCRF

7.4 Visit 3 - 12 weeks after Visit 1

Study procedures include the following assessments:

- Record any malfunctions/complaints, of device as applicable
- Assess and record any new AE, if this has not been done immediately and/or changes to ongoing AE/SAEs since the previous visit.
- Download child's BG data and review
 - o Intervention Sites: review ACCU-CHEK Connect Diabetes Management data
 - Control Site(s) review usual care SMBG data
- Discuss SMBG download with patient and parent/caregivers and collaboratively agree on therapy changes (pharmacologic and/or behavioral) and modify SMBG regimen, if needed.
- Discuss any change in software, devices, or apps used to manage diabetes or monitor child w/diabetes remotely
- Collect height and weight

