9.2.2 Symptomatic Hypoglycemia Episode

A symptomatic hypoglycemia episode is defined as an AE with symptoms consistent with hypoglycemia and may be confirmed by blood glucose readings below 70 mg/dL (3.9 mmol/L).

Symptoms might include but are not limited to: sweating, dizziness, light-headedness, tremors, nervousness, hunger, headaches, weakness or tiredness.

Symptomatic hypoglycemia is considered an expected and captured AE, as described in Section 9.3.1.1.

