11.6 Safety Analysis

All AEs will be coded using the Medical Dictionary for Regulatory Activities (MedDRA). Only AEs occurring after the start of the ACCU-CHEK [®] Connect Online Diabetes Management System will be included in the AEs tables.

Summaries of incidence rates (frequencies and percentages) of individual AEs by MedDRA System Organ Class and Preferred Term will be prepared. Such summaries will be displayed for all AEs, AEs by maximum severity, AEs by strongest causality to study device (and any associated pump devices), and AEs leading to withdrawal of study device.

Deaths, other SAEs and AEs leading to withdrawal will be listed separately.

Episodes (numbers) of the following AEs will be summarized:

- Symptomatic hypoglycaemia
- Severe hypoglycaemia (SAEs)

Diabetic Ketoacidosis (SAEs)

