5.6 Safety Analyses

The patient incidence of adverse events will be summarized by intervention group, MedDRA System Organ Class and Preferred Term. Such summaries will be displayed for all AEs, AEs by maximum severity, AEs by strongest causality to study device (and any associated pump devices), and AEs leading to withdrawal of study device. A separate analysis of the patient incidence of symptomatic hypoglycemia, severe hypoglycemia (SAE), and diabetic ketoacidosis (SAE) will also be presented.

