Table 2.7.2.2	Exit Questionnaire: Usability Child with Diabetes ITT Population
Table 2.8.1.1	Exit Questionnaire: Satisfaction Parent/Caregiver of Child with Diabetes FAS Population
Table 2.8.1.2	Exit Questionnaire: Satisfaction Parent/Caregiver of Child with Diabetes ITT Population
Table 2.8.2.1	Exit Questionnaire: Satisfaction Child with Diabetes FAS Population

Roche Diabetes Care, Inc

Table No.	Title
Table 2.8.2.2	Exit Questionnaire: Satisfaction Child with Diabetes ITT Population
Table 2.9.1.1	End of Study Questionnaire: Preference Parent/Caregiver of Child with Diabetes FAS Population
Table 2.9.1.2	End of Study Questionnaire: Preference Parent/Caregiver of Child with Diabetes ITT Population
Table 2.9.2.1	End of Study Questionnaire: Preference Child with Diabetes FAS Population
Table 2.9.2.2	End of Study Questionnaire: Preference Child with Diabetes ITT Population
Table 2.10.1.1	School Nurse Questionnaire: Preference FAS Population
Table 2.10.1.2	School Nurse Questionnaire: Preference ITT Population
Table 2.10.2.1	School Nurse Questionnaire: Usability FAS Population
Table 2.10.2.2	School Nurse Questionnaire: Usability ITT Population
Table 2.10.3.1	School Nurse Questionnaire: Satisfaction FAS Population
Table 2.10.3.2	School Nurse Questionnaire: Satisfaction ITT Population
Table 2.11.1.1	HCP Questionnaire: Preference FAS Population
Table 2.11.1.2	HCP Questionnaire: Preference ITT Population
Table 2.11.2.1	HCP Questionnaire: Usability FAS Population
Table 2.11.2.2	HCP Questionnaire: Usability ITT Population
Table 2.11.3.1	HCP Questionnaire: Satisfaction HCP Eligibility Population
Table 3.1	Summary of All Adverse Events by MedDRA SOC and Preferred Term Safety Population

Roche Diabetes Care, Inc

Table No.	Title
Table 3.2.1	Summary of All Adverse Events by Maximum Severity Safety Population
Table 3.2.2	Summary of All Adverse Events by Strongest Causality to Study Device Safety Population
Table 3.2.3	Summary of All Adverse Events Leading to Withdrawal from the Study Safety Population
Table 3.3	Summary of Symptomatic Hypoglycemia, Severe Hypoglycemia and Diabetic Ketoacidosis Safety Population

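### Symptomatic hypoglycaemia is tabulated by arm, but neither document says how episodes are to be elicited: the diary in Protocol 9.2 appears nowhere else, and scheduled enquiry is generic and 11 to 12 weeks apart

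*Protocol*

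**What the plan says.** - **Route of documentation.** Protocol 9.2 gives two alternatives. The first is that the episode "will be documented by the subject him-/herself in his/her individual Subject Diary, if applicable". The second, later in that sentence, refers the reader to other parts of the protocol: "or will be defined specifically by the study procedure e.g. in the visit description of this study protocol".
- **Status of the event.** Protocol 9.2.2: "Symptomatic hypoglycemia is considered an expected and captured AE, as described in Section 9.3.1.1". Section 9.3.1.1 then requires an AE form in the eCRF. The definition rests on symptoms, and glucose evidence is optional (the episode "may be confirmed by blood glucose readings below 70 mg/dL (3.9 mmol/L").
- **Enquiry at visits.** Protocol 7.3 (week 1 call): "Record any adverse events (AEs) since last visit, if this has not been done immediately". Section 7.4 (Visit 3) has a similar line with the same proviso. Section 7.5 (Visit 4) asks for new or changed events since the previous visit. None of these sections mentions hypoglycaemia.
- **Reporting.** Protocol 11.6: "Episodes (numbers) of the following AEs will be summarized", with symptomatic hypoglycaemia first on the list. SAP 5.6: "A separate analysis of the patient incidence of symptomatic hypoglycemia, severe hypoglycemia (SAE), and diabetic ketoacidosis (SAE) will also be presented". The SAP table list has Table 3.3, "Summary of Symptomatic Hypoglycemia, Severe Hypoglycemia and Diabetic Ketoacidosis Safety Population".

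**The concern.** Section 9.2 points to two places for the method of capture, and neither contains one. How many symptomatic episodes reach the database then depends on how each site asks and on what each family remembers and volunteers.

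This matters more here than in a blinded, individually randomised trial. Whole sites are allocated, and Protocol 5 says the allocation is communicated to the investigators, so each site's way of asking is nested within one arm. The intervention also adds things that could change what is noticed or mentioned: real-time data sharing (Protocol 1.1), logging of contextual data in the app (3.1), and follow-up about problems with the system at Visits 2, 3 and 4 (7.3 to 7.5). If capture differs between arms, the symptomatic row of Table 3.3 could show an excess that is not real or hide one that is. No later analysis can repair the way symptoms were elicited.

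**Working it through.** **1. Is either route in 9.2 filled?** A Subject Diary is named in 9.2. It is absent from the Schedule of Assessments, the visit procedures (7.2 to 7.6), subject training (7.8), data collection (7.11), the supplied materials (13.1.2, an open-ended list) and the SAP's data sources (SAP 2.2). The visit descriptions do provide a route in both arms, but only a general AE enquiry. No wording, reference period or count for symptomatic episodes is given.

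**2. How far apart are the scheduled enquiries?** Inputs are the visit weeks and windows in the Schedule of Assessments, in days from Visit 1: Visit 2 = 7 ± 2 (5 to 9), Visit 3 = 84 ± 14 (70 to 98), Visit 4 = 168 ± 14 (154 to 182).

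| Gap | Shortest | Nominal | Longest |
|---|---|---|---|
| Visit 2 to 3 | 70 − 9 = 61 d (8.7 wk) | 84 − 7 = 77 d (11 wk) | 98 − 5 = 93 d (13.3 wk) |
| Visit 3 to 4 | 154 − 98 = 56 d (8 wk) | 168 − 84 = 84 d (12 wk) | 182 − 70 = 112 d (16 wk) |

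The two long gaps cover (168 − 7)/168 = 161/168 = 96% of nominal follow-up. Protocol 14 does not count window departures as deviations, so longer gaps are possible.

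**3. Can other data fill the hole?** Not for this event. SAP 3.5.2.2 derives the percentage of readings below 70 mg/dL, which carries no symptom information. Under Protocol 9.2.1 and 9.3.1.2 a low reading without symptoms is not entered as an AE.

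**4. What could unequal capture do?** The documents give neither an event rate nor a capture proportion, so everything in this step is assumed and illustrative.

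- Volume: at 0.5 to 2 symptomatic episodes per child-week, the number of episodes to be reported runs from 150 × 24 × 0.5 = 1,800 to 200 × 24 × 2 = 9,600.
- Episode counts (the Protocol 11.6 measure): with equal true rates and capture of 50% against 30%, the apparent ratio is 0.50/0.30 = 1.67.
- Patient incidence (the SAP 5.6 measure), same capture, Poisson episodes captured independently:
  - At 0.5 per week (12 expected in 24 weeks): (1 − e^−6)/(1 − e^−3.6) = 0.998/0.973 = 1.03.
  - At 0.1 per week (2.4 expected): (1 − e^−1.2)/(1 − e^−0.72) = 0.699/0.513 = 1.36.
- Patient incidence if whole families report or do not: 90% against 70% gives 0.90/0.70 = 1.29, and 90% against 50% gives 1.80.

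The effect therefore depends heavily on which of the two measures is tabulated and on how under-reporting arises. At the higher rates patient incidence is near its ceiling. It is then less sensitive to random under-reporting, but also to a real difference in the number of episodes.

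**The case against.** The strongest case against has five parts.

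- **The diary is conditional.** A reader might infer that the protocol requires a diary and then fails to supply it. The text does not support that. Section 9.2 says it applies only where applicable and offers an alternative, and the materials list in 13.1.2 is not exhaustive. This is unresolved wording, not a missing mandatory tool. This part stands.
- **Recall is not the only route.** The lines for Visits 1 to 3 presuppose that some events are recorded when they happen, and Protocol 7.7 adds unscheduled visits. This stands too, but no tool is described that would support recording at the time.
- **Differential capture is not shown.** A reader might infer that capture does differ by site and arm. The documents do not say so. The AE schedule is the same in both arms, control meters also store readings that are downloaded and reviewed with families at Visits 3 and 4, and app sharing is described as optional. With randomised sites, differences in recording habits are a chance imbalance among 8 to 13 clusters, not systematic confounding. What stands is a risk: the intervention-only features are real, and no common script offsets them.
- **An objective comparison exists.** The percentage of readings below 70 mg/dL is compared between arms by ANCOVA (SAP 5.5.2, Tables 2.5.6.1 and 2.5.6.2). Severe hypoglycaemia and ketoacidosis are SAEs with immediate reporting (Protocol 9.6). SAP 5.6 specifies no test between arms. All true, and this limits the point to one row of Table 3.3. That row is still set out by group and will be read as a comparison.
- **The remedy is one of several.** A properly defined diary, or a standard wording of the existing AE question, would also be defensible. The scripted count is preferred because it needs no new tool or visit.

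**Conclusion.** The point holds in a limited form. Neither document sets out how symptomatic hypoglycaemia is to be elicited, and the only subject-level tool named in 9.2 is not described or scheduled. Unless an episode is recorded immediately or at an unscheduled visit, it depends on unstandardised, unblinded enquiry 11 and 12 weeks apart nominally, and up to 16 weeks apart within the windows. In an open, cluster-randomised design with intervention-only features, capture may differ by site and arm, so the symptomatic row of Table 3.3 cannot be relied on as a comparison.

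The gap lengths follow directly from the schedule. The size of any bias does not: the ratios of 1.03 to 1.80 rest entirely on assumed rates and capture proportions. The 1.67 in particular applies to episode counts only and should not be quoted as an expected bias. The primary endpoint is untouched.

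A separate inconsistency is plain from the text: Protocol 11.6 promises numbers of episodes, while SAP 5.6 promises patient incidence.

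**What to change.** 1. In Protocol 9.2, delete the diary reference and point to the visit sections.
2. In 7.4 and 7.5, add one scripted question, identical in both arms: the number of symptomatic episodes in a short fixed period, for example the previous 4 weeks. It is asked before any glucose data are opened and entered as a count.
3. In SAP 5.6 and Table 3.3, present this count by arm beside the full-period AE summary. Label spontaneously reported symptomatic episodes as not reliably comparable between arms. Leave full-period reporting of severe hypoglycaemia and ketoacidosis as it is.
4. Reconcile Protocol 11.6 with SAP 5.6 by stating whether episodes, patients or both are tabulated.

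The cost is one eCRF item at two existing visits, plus wording in both documents. The limits are real: two 4-week periods cover 8 of 24 weeks, there is no baseline count, and the answer is still unblinded recall. The change makes the enquiry uniform and shortens the recall period. It does not make the outcome objective.

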9.2.1 Asymptomatic Hypoglycemia Episode

An asymptomatic hypoglycemic episode is defined as a low blood glucose reading below 70 mg/dL (3.9 mmol/L) without symptoms and is considered as a non-captured expected AE described in Section 9.3.1.2.

9.2.2 Symptomatic Hypoglycemia Episode

A symptomatic hypoglycemia episode is defined as an AE with symptoms consistent with hypoglycemia and may be confirmed by blood glucose readings below 70 mg/dL (3.9 mmol/L).

Symptoms might include but are not limited to: sweating, dizziness, light-headedness, tremors, nervousness, hunger, headaches, weakness or tiredness.

Symptomatic hypoglycemia is considered an expected and captured AE, as described in Section 9.3.1.1.

9.2.3 Severe Hypoglycemia Episode

A severe hypoglycemia episode is defined as symptoms in loss of consciousness and/or seizures resolving upon administration of glucose or glucagon by another person (only third party assistance). A blood glucose value below 36 mg/dL (2.0 mmol/L) might be available, but is not mandatory (if no assistance, then not considered Severe Hypoglycemia).

Such episodes are defined as SAEs and, thus, they must follow the SAE reporting pathway via the eCRF (or be faxed).

9.2.4 Hyperglycemia Episode

Hyperglycemia is defined as high blood glucose readings, a recommended threshold to intervene could be defined as values above 240 mg/dL (13.3 mmol/L). However, investigators should consider the condition of the individual subject.

Only hyperglycemia episodes in combination with medical intervention or additional diagnostic procedures have to be documented as AE in the eCRF, as described in Section 9.3.1.1.

9.2.5 Diabetic Ketoacidosis

Diabetic Ketoacidosis is defined as any symptoms such as polydipsia, polyphagia, polyuria, nausea, or vomiting; and presence of serum ketones, or moderate or large urinary ketones; and either arterial blood pH <7.3 or serum bicarbonate <15 mg/L and treated as directed by the subject's physician.

Such episodes are also defined as SAEs and, thus, they must follow the SAE reporting pathway via the eCRF (or be faxed).

[figure not shown]

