9.3.1 Expected Adverse Events

9.3.1.1 Captured Expected Adverse Events

The following expected AEs may occur at any time in the course of managing diabetes. Immediate or short term risks to subjects from some of these expected AEs are higher than those identified under Non-Captured Expected AEs.

Therefore, for the purposes of this study, the following expected AEs will be considered captured expected AEs and the AE Form in the eCRF needs to be completed:

- Symptomatic hypoglycemia episodes (see Section 9.2.2).
- Hyperglycemia in combination with medical intervention..
- Ketosis and ketoacidosis.

These captured expected AEs will be handled as follows:

Subjects will be instructed to follow their personal physicians' instructions for management of low and high blood glucose values or otherwise as instructed by the Investigator.

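### As printed, the bicarbonate limit in the diabetic ketoacidosis definition (about 0.25 mmol/L) cannot be met in practice, so only arterial pH can qualify an event under Protocol 9.2.5

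*Protocol*

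**What the plan says.** Protocol 9.2.5 builds the DKA definition from elements that must all be present: symptoms, ketones in serum or at a stated level in urine, treatment under the physician's direction, and an acid-base finding. There are two alternatives for the acid-base finding. One is an arterial pH under 7.3; the other is "serum bicarbonate <15 mg/L". The section then adds "Such episodes are also defined as SAEs", so meeting the definition is enough to make an event serious, and Protocol 9.6 requires immediate reporting of SAEs.

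Two other parts of the protocol reach ketoacidosis without using this limit:

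- **Protocol 9.1.2**, the general SAE definition, covers any adverse event with serious deterioration in health. Its listed results include a threat to life, treatment given to avert one, and "An in-patient or prolonged hospitalization".
- **Protocol 9.3.1.1** lists "Ketosis and ketoacidosis" among the expected events that need an AE Form, with no laboratory limit and no cross-reference to 9.2.5.

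DKA is one of three event types singled out for its own safety summary. Protocol 11.6 counts episodes. SAP 5.6 states: "A separate analysis of the patient incidence of symptomatic hypoglycemia, severe hypoglycemia (SAE), and diabetic ketoacidosis (SAE) will also be presented". SAP Table 3.3 is the matching output. The definitions in SAP section 3 do not cover DKA, so Protocol 9.2.5 is the only definition behind that table.

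**The concern.** Mass per litre is an odd unit for a bicarbonate limit, and the number attached to it converts to a very small molar concentration. The two acid-base findings are alternatives. If one of them can never be satisfied, the definition quietly narrows to the other, and an event with a bicarbonate result but no arterial sample cannot qualify.

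This is a working threshold, because it decides whether an event is automatically serious and whether it belongs in one line of a planned safety table. A site that applies the text literally and a site that silently substitutes another unit could classify the same event differently. An analyst building Table 3.3 would have no written rule for settling the difference.

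**Working it through.** **Inputs**

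- Limit and unit: 15 mg/L, from Protocol 9.2.5. It appears once, with no second unit and no derivation, so the plan has no figure of its own to reproduce here.
- Molar mass of bicarbonate (HCO3-): 1.008 + 12.011 + 3 × 15.999 = 61.016, rounded to 61.02 g/mol. This is a chemical constant that the documents do not give.
- Molar mass of glucose, used only to check the neighbouring units: 180.156 g/mol, also a chemical constant.

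**Step 1. Check the neighbouring units.** The glucose limits in Protocol 9.2 are printed in two units, so they can be tested with mmol/L = (mg/dL × 10) / 180.156.

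| Protocol section | Printed mg/dL | Computed mmol/L | Printed mmol/L |
|---|---|---|---|
| 9.2.1 | 70 | 3.89 | 3.9 |
| 9.2.3 | 36 | 2.00 | 2.0 |
| 9.2.4 | 240 | 13.32 | 13.3 |

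All three agree. Among the limits checked in this section, the problem is confined to bicarbonate.

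**Step 2. Convert the bicarbonate limit.** mmol/L = (mg/L) / 61.02, so 15 / 61.02 = 0.246 mmol/L.

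**Step 3. Try other readings of the same number.** These show scale only and do not say which unit is intended.

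- Read as mg/dL: 150 mg/L / 61.02 = 2.46 mmol/L, ten times the printed limit.
- Read as mmol/L: 15 × 61.02 = about 915 mg/L, which is 915 / 15 = 61 times the printed limit.

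**Step 4. Follow one event through the text.** Take a case with symptoms, ketones, treatment and a bicarbonate result, but no arterial pH.

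| Rule | Depends on the bicarbonate limit? | Result for this case |
|---|---|---|
| 9.2.5, DKA definition | Yes | Not met as written, so no automatic SAE |
| 9.1.2, general SAE criteria | No | SAE if any criterion is met |
| 9.3.1.1, captured expected events | No | AE Form required |
| Protocol 11.6, SAP 5.6 and Table 3.3 | Through 9.2.5 | No stated rule if the case is serious under 9.1.2 but fails 9.2.5 |

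Two gaps remain. A case that meets none of the general criteria loses its automatic SAE route and may be entered only as a non-serious event. A case that is serious on general grounds has no written rule on whether it counts as DKA in the summary.

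**Step 5. Size.** The count affected is the number of otherwise qualifying events with bicarbonate but no arterial pH. The documents give neither a DKA rate nor that share, so the share could lie anywhere from 0% to 100% and no count follows.

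**The case against.** The strongest reply is that little is lost in practice. Protocol 13.2 describes sites staffed by pediatric endocrinologists and pediatric diabetes specialists, who may well read past an implausible unit. Every ketoacidosis case is recorded under 9.3.1.1, coded, tabulated by preferred term (SAP Table 3.1) and listed as serious or non-serious. Neither document plans a test of DKA between arms, and no efficacy estimate, power figure or error rate is touched. All of this stands, and it is why the point is of low severity. It does not repair the definition: if sites supply their own unit, the rule actually applied is unwritten.

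Two cautions also stand. That 0.25 mmol/L is unattainable comes from general physiology and not from the documents. And because the text was extracted from a PDF and the limit appears only once, a reading fault cannot be fully excluded. The correctly rendered glucose units nearby make one less likely.

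Two stronger readings are tempting, and the documents support neither:

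- **A reader might infer that bicarbonate-only cases escape SAE reporting altogether.** They do not. The general criteria in 9.1.2 apply whatever the bicarbonate value, and 9.2.5 only adds an automatic route.
- **A reader might infer bias between arms, because whole sites are randomized.** SAP 2.1.1 allocates 8 to 13 sites 1:1, which is 4 per arm with 8 sites and 6 and 7 with 13. Each arm therefore contains several sites, and nothing links how a site reads the unit to the arm it was given.

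**Conclusion.** Wrong as written; low severity, affecting safety classification only. The printed limit equals 0.246 mmol/L. On the assumption that no patient's serum bicarbonate falls that low, the bicarbonate alternative is empty and only arterial pH can satisfy the acid-base element of 9.2.5. What is lost is the automatic SAE route for cases documented by bicarbonate alone, together with consistent counting in the DKA (SAE) summaries. Reporting under the general SAE criteria and capture as an adverse event both survive. The number of events affected cannot be derived from the documents, and no difference between arms is shown.

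**What to change.** 1. Check the unit against the source page of the protocol, to exclude a text-extraction fault.
2. If the unit is as printed, have the sponsor's medical lead confirm the intended unit, and correct 9.2.5. No clinical threshold is proposed here.
3. Reconcile 9.2.5 with the ketosis and ketoacidosis item in 9.3.1.1, for example by cross-reference, so that it is clear which events are automatically serious.
4. Apply that one definition in the SAE form and in the programming behind SAP Table 3.3. Also state how an event is counted if it is serious under 9.1.2 but does not meet 9.2.5. The SAE form is not among the documents, so whether it repeats the unit should be checked.

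**Cost:** a small protocol amendment and a site notice. Protocol 12.7 sends modifications to the IRB and requires written approval before they take effect, apart from changes that remove an immediate hazard or are purely logistical or administrative. IRB submission should therefore be planned for. No new data collection is needed.
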